#### 5.4 Taking test sensitivity, specificity and cross-reactivity into account

PCR tests can be regarded as effectively 100% specific, but they have a short detection window, which varies between individuals. We refer to this as the test's persistence distribution. Serological tests vary in their specificity and sensitivity. Failures of specificity (false positives) can arise for several reasons. While some may be due to a random signal that has exceeded the test's threshold, other false positives may be due to cross-reaction to antibodies to related viruses. Currently available DENV and ZIKV IgM tests react to each other's IgM, and to other flavivirus IgM. We can therefore anticipate that ZIKV and DENV IgM test specificity might vary between collaborating centers, reflecting the geographical distribution of other viruses to which they are cross-reactive. In addition, although IgM antibody is usually assumed to persist for 12 weeks, in some individuals it may persist for many months. Therefore, if IgM is due to an infection acquired many months before the pregnancy, we might regard it as an *analytic* true positive, but a *diagnostic* false positive.

Information on the effective sensitivity and specificity of IgG and IgM assays in different centers is currently incomplete, but will be systematically developed under the ZIKA-VID program. Sources of data on properties of diagnostic tests, for use in ZIKA-VT data analyses, will be updated regularly (see *Appendices 3 & 4*).

Reliable estimates of the sensitivity and specificity of each individual test are not, by themselves, enough to determine the probability that a woman has experienced an infection in pregnancy given her test results. Each woman will be tested on multiple occasions, and on multiple tests. Interpretation of these sequences of tests is complex as we can anticipate there are strong correlations, conditional on true infection status, both between tests results at the same time, and between tests of the same type over time. Rules for determining whether a sequence of tests and clinical findings should be considered as a reflecting a "confirmed", "definite" or "possible" maternal infection will be drawn up by the Expert Diagnostics Group (*Appendix 1*).

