### 7.5 Using ZIKA-VT data to update prior information on test persistence

The previous section has shown how, given information on test persistence, the date of a positive PCR or IgM test informs the GA of maternal infection. In this section, we show how to estimate the distribution of test persistence from ZIKA-VT data, or, more usefully, how to update any prior information available.

Simplifying assumptions have been made for purposes of clarity and in order to keep the notation minimal: for example, that the date of onset of symptoms is taken to be the date of the onset of infection, and that tests are positive from that date. Adjustments can, and will, be made to accommodate these factors, but at this stage greater veracity would be at the expense of clarity.

 $F(d,\theta)$  is defined for d=1,2...D where D is the maximum possible duration of that marker. The data generated by ZIKA-VT and similar studies is *doubly interval censored*, because in most cases neither the onset of the marker response, nor the end of the marker response, is observed. Methods for analysis of doubly interval censored data have been published [5, 6] and have been applied to the timing of maternal infection in the context of congenital toxoplasmosis [7, 8]. A recent paper [9] includes a brief up-to-date review of the most commonly used methods.

ZIKV and the ZIKA-VT protocol have features that require extensions and modifications to existing methods. First, not only is incidence changing over time, but each individual woman is exposed to a different incidence which varies over the course of her pregnancy. Second, information on multiple markers in multiple types of samples will need to be processed simultaneously.

We begin with an analysis for a single marker, then we consider how to handle variables that might affect persistence, such as previous infection or the presence of symptoms, and finally the joint analysis of multiple markers.

[figure not shown]

Author: [name] (UNIVBRIS)

21

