#### 7.5.1 Estimating the persistence distribution of a single test

The objective here is to estimate the parameters  $\theta$  of the persistence distribution  $F(d,\theta)$  from data  $U_{Li}$ ,  $U_{Ri}$ ,  $W_{Li}$ ,  $W_{Ri}$  for every woman i, taking the following general form:

This represents a sequence of tests -++-, starting with a "last –ve" before the infection occurs at  $U_L$  and a first +ve after the infection at  $U_R$ . The onset of infection is within this interval. The date at which the test turns negative is between the last +ve at  $W_L$  and the first –ve at  $W_R$ . In practice, we may not observe a sequence -++- in a series of IgM or PCR tests in every woman. However, in combination with the occurrence of symptoms and the results of IgG tests, it will be possible to construct definite dates  $U_{Li}$ ,  $U_{Ri}$ ,  $W_{Li}$ ,  $W_{Ri}$  for every woman i who tests +ve on either IgM or PCR. For example, if symptoms occur at time T then  $U_{Li} = U_{Ri} = T$ ; if no final –ve test is observed, then  $W_{Ri} = W_{Li} + D$ ; if no initial –ve test is observed, then  $U_{Li} = U_{Ri} - D$ ; and so on. Note, also, that if a baby born to women i is confirmed to be congenitally infected, then this information requires that  $-2 \le t \le G$ ; in other words,  $U_{Li} \ge -2$  and  $U_{Ri} \le G_i$ .

If the data indicates that the GA of maternal infection is at t,  $U_{Li} \le t \le U_{Ri}$ , then the probability of the data given that t = T is:

$$\Pr(U_{L_i}, U_{R_i}, W_{L_i}, W_{R_i} \mid t = T, \theta) = \begin{cases} F(W_{R_i} - T - 1, \theta) - F(W_{L_i} - T - 1, \theta) & U_{L_i} \le T \le U_{R_i} \\ 0 & \text{otherwise} \end{cases}$$

Therefore, averaging over the distribution of maternal infection  $\pi_i(t)$ , the likelihood for the data is:

$$\Pr(U_{Li}, U_{Ri}, W_{Li}, W_{Ri} \mid \pi_i(t), \theta) = \sum_{i} \pi_i(t) (F(W_{Ri} - t - 1, \theta) - F(W_{Li} - t - 1, \theta)), U_{Li} \le t \le U_{Ri}$$

If the onset of infection at  $t_S$  is observed,  $U_{Li} = t_S = U_{Ri}$  and  $\pi_i(t_S) = 1$ , and the likelihood reduces to the standard likelihood for right censored or right interval censored data.

Author: [name] (UNIVBRIS)

22

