#### 7.5.3 Estimating the persistence distributions of multiple tests

The ZIKA-VT protocol provides for

Author: [name] (UNIVBRIS)

23

- (i) PCR, IgM, and IgG tests on women with symptoms,
- (ii) PCR on all IgM+, IgG seroconversions, and rises in IgG titer.
- (iii) Repeat PCR, IgM, and IgG tests at the prescribed intervals until a first PCR-, IgM-, IgG falling titer, respectively.
- (iv) Use of serum, saliva, and urine samples.
- (v) Avidity tests may be used to determine if an infection is primary or secondary; this also carries information on timing of infection

Thus, each woman's record is likely to consist of a series of results on at least three tests and possibly more if more than one assay of each type is used.

The analysis above for a single test is readily extended to two or more tests k=1,2...K. The data on each individual i now consists of K sets of implied -++- sequences denoted  $U_{Li_k}, U_{Ri_k}, W_{Li_k}, W_{Ri_k}$ , and the parameter set is expanded to accommodate K distributions  $F_k(d,\theta_k)$ . The likelihood for the persistence tests for woman i is then:

$$\Pr\left(\begin{array}{c} (U_{Li_{k}}, U_{Ri_{k}}, W_{Li_{k}}, W_{Ri_{k}}) \mid \pi_{i}(t), \theta_{k} \end{array}\right) = \sum_{t} \pi_{i}(t) \prod_{k} \left( F_{k}(W_{Ri_{k}} - t - 1, \theta_{k}) - F_{k}(W_{Li_{k}} - t - 1, \theta_{k}) \right) \quad Max_{k}(U_{Li_{k}}) \leq t \leq Min_{k}(U_{Ri_{k}})$$

Note that, in this framework, the date of symptoms and the dates of short persistence tests such as PCR, are highly informative about the persistence distributions of longer persistence tests such as IgM and rising IgG.

Extension to multiple tests, use of a variety of tests, and changes in which tests are used, raises questions about the numbers of parameters that may need to be estimated. Our initial strategy will be to assume that the persistence distributions of all tests of the same type (PCR, IgM, rising IgG) have the same underlying parametric or semi-parametric form, with persistence distributions that differ only by a single parameter, for example based on a proportional hazards assumption. This constant would be estimated from the data. Persistence distributions for different *samples* (serum, saliva, urine) on the same test will be treated the same way.

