## 7.6 Accounting for imperfect test sensitivity and specificity, and cross-reactivity

As noted earlier, we need to calculate for each woman recruited into ZIKA-VT, the probability that she was infected in pregnancy, and the distribution of GA when this infection occurred, if it occurred at all, based on tests with imperfect accuracy.

Author: [name] (UNIVBRIS)

24

For example, a sequence of four ZIKV IgM- results throughout pregnancy, assuming there were no IgG, PCR tests and no symptoms, would be scored as "No evidence of maternal infection in pregnancy" in basic analyses, but there is a possibility that they are all false -ves.

As long as the testing algorithm is relatively sensitive, say 95% or more, the bias in estimates of the vertical transmission due to false -ves is likely to be negligible. A small proportion (<5%) of maternal infections would be missed from the denominator, but their babies will not be followed up, and so would also be missed from the numerator. The exception to this would be if they are not only congenitally infected but their congenital infection is apparent. But it can be shown that, on current evidence, this would lead to only a very slight over-estimation of the VTR.

The difficulties posed by false *positive* IgM tests are, however, far more serious. If the specificity of an IgM test is 95%, then 5% of uninfected mothers will receive false +ve results, and will be considered infected in pregnancy. If 10% of women are infected in pregnancy, then, for every 15 women considered as infected in pregnancy, only (approximately) 10 would be truly infected, and the vertical infection rate will be underestimated by a factor of 1.5. If incidence is lower, and only 1% of women are infected in pregnancy, then only 1 in 5 women being followed are truly infected and the vertical transmission rate will be underestimated by a factor of 5.

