#### 8.2 Analyses of properties of diagnostic tests

As noted earlier the ZIKA-VT and ZIKA-VID programs are inter-related and the analyses set out in *Section 7.5* will provide the definitive information on the persistence of IgM and other tests.

However, the population epidemiology data collected by ZIKA-VT also provides an opportunity for *supportive* analyses of test persistence, sensitivity and specificity. Results should be compared with the more formal evaluations undertaken as part of ZIKA-VID, which will comprise evidence from published literature as well as findings from *de novo* field work.

8.2.1 Average persistence of IgM. Given estimates of IgM prevalence (section 8.1.5) and incidence of primary infections based on seroconversion (section 8.1.4) or changes in cumulative incidence (section 8.1.6), estimates of the average persistence of IgM can be estimated by dividing IgM prevalence by IgM incidence.

We anticipate that IgM persistence may differ in women with previous ZIKV or DENV infections. If these women can be identified by avidity tests it will be possible to generate separate estimates of average IgM persistence for primary and secondary infections

8.2.2 Sensitivity and cross-reactivity of IgM and IgG tests. Estimates of sensitivity will be available for IgM and IgG tests in women with infections confirmed by PCR, and from cases where tests failed to detect infections in mothers of babies in whom congenital infection is demonstrated.

8.2.3 Specificity of IgM and IgG tests. Specificity of IgG tests can only be estimated in populations which are known to have not been exposed to the infection in question: this means that data collected in ZIKA-VT is not relevant to estimates of IgG specificity. However, IgM specificity can be studied by observing the relationship between the proportion of tests which are positive and the surveillance data over the previous 12 months. IgM persistence is believed to be about 12 weeks on average, so that an IgM+ occurring at a time when surveillance sources indicate there has been no virus circulating for over 4 or 5 months are highly likely to be false positives from a diagnostic point of view, whether due to persistent antibody, cross-reactions, or other factors; although it will be important to be able to rule out foreign travel before making these inferences. Data of this sort will be of great importance in defining the tails of the persistence distributions of IgM tests

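### The persistence likelihood in SAP 7.5.1 and 7.5.3 uses women caught positive but never conditions on that, which biases marker persistence

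*SAP*

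**What the plan says.** Section 7.5.1 sets out the data for one marker as a last negative U_L, a first positive U_R, a last positive W_L and a first negative W_R. Onset lies between the first two; "The date at which the test turns negative is between the last +ve at" W_L and the first negative W_R. The dates are to be constructed "for every woman i who tests +ve on either IgM or PCR". Each woman contributes the sum over t of π_i(t)[F(W_R−t−1) − F(W_L−t−1)]. When onset is observed, "the likelihood reduces to the standard likelihood for right censored or right interval censored data".

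Section 7.5.3 multiplies these bracketed terms over markers inside one sum over a shared onset t. It also sets the testing routes: all three test types for symptomatic women, and "PCR on all IgM+, IgG seroconversions, and rises in IgG titer". Section 5.4 says of PCR tests that "they have a short detection window, which varies between individuals".

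Section 7.5 says of its simplifications that "Adjustments can, and will, be made to accommodate these factors". The examples given are the dating of onset and the start of positivity. Selection on a positive result is not mentioned in 7.5 to 7.5.3.

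**The concern.** A woman can be seen positive only if her response lasts until the next test. Long responses are therefore over-represented among the women analysed, and a likelihood that ignores this treats them as typical.

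The stake is more than the persistence curve. Section 5.3 treats persistence as critical for dating maternal infection, section 7.4 puts it directly into π_i(t), and section 7.1 uses π_i(t) to estimate V(t). Section 8.2 regards the 7.5 analysis as the definitive source on persistence. Section 4 also claims that the plan gives unbiased estimates whatever the scheduling of maternal tests. A bias that changes with the gap between tests breaks that claim.

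**Working it through.** The SAP gives no figure for this bias, so there is nothing to reproduce.

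**Inputs**
- Mean IgM persistence m₀ = 12 weeks: section 8.2 says "IgM persistence is believed to be about 12 weeks on average".
- Test gap h: the SAP gives no schedule. Section 7.6 uses "a sequence of four ZIKV IgM- results throughout pregnancy" as an illustration, which over roughly 40 weeks suggests about 10 weeks. I take 4, 8 and 12 weeks as assumptions.
- Distribution: exponential first, then Weibull, which section 7.5.2 names. Onset is flat within the gap and tests are perfect.
- PCR mean: not in the SAP. I assume 2 weeks where needed.

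**Step 1: what is missing.** Write q = exp(−h/m), and let K be the number of further positive visits after the first. Averaging the printed term over a flat onset gives

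q^K(1−q) × (m/h)(1−q).

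The correct contribution, given that she was caught positive, is q^K(1−q). The extra factor (m/h)(1−e^(−h/m)) is exactly the probability of being detected. It rises with m, so the estimate is pulled upward.

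**Step 2: the size for IgM, exponential.** Among detected women E[K] = 1/(e^(h/m₀)−1). Setting the expected score of the printed likelihood to zero gives

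1/(e^(h/m₀)−1) = 2/(e^(h/m)−1) − m/h.

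| h (weeks) | P(detected), m₀=12 | Left side | Solution m | Check of right side |
|---|---|---|---|---|
| 4 | 3(1−e^(−1/3)) = 0.85 | 2.528 | 13.9 | 6.008 − 3.480 |
| 8 | 1.5(1−e^(−2/3)) = 0.73 | 1.055 | 15.8 | 3.026 − 1.971 |
| 12 | 1(1−e^(−1)) = 0.63 | 0.582 | 17.6 | 2.051 − 1.469 |

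Simulation of the same setting gives 13.8, 15.8 and 17.6. With the detection factor divided out, the equation becomes 1/(e^(h/m₀)−1) = 1/(e^(h/m)−1), so m = 12 at every gap; simulated estimates return to 11.9–12.0.

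**Step 3: other shapes.** For Weibull shape 2 over the same gaps, the estimate runs from 12.2 to 13.8 weeks. The direction is the same and the size much smaller.

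**Step 4: symptomatic women.** Those tested at onset are not subject to this selection. With exponential IgM and a 10-week gap, the estimate is 16.7, 15.4, 13.9, 12.7 and 12.0 weeks when 0, 20, 50, 80 and 100% of women are of this kind.

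**Step 5: PCR.** Treated as a lone screened marker with an assumed mean of 2 weeks and flat π_i(t), in weekly time, the estimate is 3.0–3.4 weeks at a 4-week gap and 7.4–7.8 at 10 weeks (Weibull shapes 1 to 2). If π_i(t) is instead weighted by survival to the positive test, exponential persistence in weekly time gives 2.25 weeks at a 4-week gap but 0.57 at 8 weeks, an under-estimate. PCR is wrong either way, but the sign is not fixed.

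**Step 6: several markers.** Because the markers share t inside one sum, dividing marker by marker over-corrects: a true 12 weeks comes back as 9.9 to 11.6. Dividing the whole sum once by the joint detection probability recovers the truth.

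**The case against.** Several defences have force.

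- A reader might infer that an IgM+ woman with a negative triggered PCR is shut out. The text does not support that: testing positive on either marker admits her, the four-date form is described as general, and its date rules are left open-ended. Setting W_L at or before onset would even give the right term, F(W_R−t−1). What is missing for her is a stated rule. Women missed on both markers do remain outside.
- A reader might also infer that PCR persistence will be inflated several-fold. The screened-PCR figures do not represent this study, where PCR goes to symptomatic women and to those triggered by IgM or IgG and is analysed jointly with IgM. Step 5 shows that even the direction depends on the reading of π_i(t).
- Section 7.5.1 allows published persistence results as informative priors, which would dilute the bias, and checks for conflict between prior and data. That check could reveal a problem but supplies no remedy. The fit statistics use the same selected women.
- Section 8.2.1 offers an independent IgM estimate, prevalence over incidence. It is labelled supportive and covers IgM only.
- The promised adjustments in 7.5 might be stretched to cover selection, but their examples concern onset and the start of positivity.

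These points narrow the size and scope. None supplies the missing conditioning for asymptomatic women found by screening.

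**Conclusion.** The likelihood is wrong as written for women found by interval screening. With flat π_i(t), IgM persistence is over-estimated: about 13.9 to 17.6 weeks against 12 if exponential, and about 12.2 to 13.8 for Weibull shape 2, at assumed gaps of 4 to 12 weeks with perfect tests, no symptomatic women and no informative prior. Real estimates would be less biased to the extent that either of the last two contributes. For PCR, mis-estimation can be asserted, but not a size; nor can a direction be asserted if π_i(t) is survivor-weighted.

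The dependence on test spacing contradicts the scheduling property claimed in section 4. The error passes into gestational age at infection and V(t). A reader might go further and conclude that the vertical transmission rate is biased by a known amount. That has not been shown: persistence acts only within the interval fixed by the tests, and surveillance data also inform timing.

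**What to change.** 1. In 7.5.1, define π_i(t) as the onset distribution before the marker result. Divide each screened woman's likelihood by her probability of being detected positive, Σ π_i(t)[1−F(U_R−t−1)].
2. In 7.5.3, state the selection event and divide the whole joint sum once by its probability under the shared onset. If all K markers must be positive, this is Σ π_i(t) Π_k[1−F_k(U_Rk−t−1)]. If one positive among markers screened at the same visit suffices, replace the product by 1−Π_k F_k(U_R−t−1). Do not divide marker by marker.
3. Where a marker was tested because of another trigger (symptoms, IgM+, seroconversion, titer rise), keep women who are negative on it, with factor F_k(t_test−t−1) inside the sum over t. Apply no detection correction for that marker.

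The cost is SAP wording, slightly more coding and somewhat wider posteriors for the persistence parameters. No new data are needed: by 7.5.3, PCR results on seroconverters and IgM+ women will already exist.

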#### 7.4 Analysis of gestational age at maternal infection

We start with an analysis that assumes perfect test sensitivity and specificity. The gestational age at the onset of maternal infection is  $\pi_i(t)$ , t in weeks. Although the period of interest is between just before conception and delivery, ie the interval  $-2 \le t \le G_i$ ,  $\pi_i(t)$  is defined over a wider interval  $-2 - D \le t \le G_i + D$ , where D is the maximum duration of a test of persistence. This is because a first IgM+ test D weeks after delivery, or an IgM- test D+2 weeks before conception, both provide information about the probability of infection during pregnancy. Because there may be a finite probability that the maternal infection occurred before conception,  $\sum_{-2 \le t \le G_i} \pi_i(t)$  can take any value

between 0 and 1. Some special cases help clarify the concepts:

7.4.1 Onset of infection marked by symptoms. If a woman has symptoms in pregnancy starting at T then  $\pi_i(t) = 1$ , if t = T and  $\pi_i(t) = 0$ , if  $t \neq T$ .

7.4.2 Seroconversion alone. If the interval is defined by seroconversion during pregnancy, ie between a last lgG- at  $t_1$  and a first lgG+ at  $t_2$ , then in the absence of any other information,

$$\pi_i(t) = 1/(t_2 - t_1 + 1)$$
, if  $t_1 \le t \le t_2$ , else 0.

7.4.3 Surveillance data alone. Alternatively, suppose there are surveillance counts M(t) of suspected or confirmed cases (of ZIKV, DENV, or CHIKV) depending on the disease being studied [4], then the "a priori" distribution of when the infection might have occurred (given that it occurred in pregnancy) can be represented as a Dirichlet distribution:

$$\pi_i(t) = \alpha(t), \quad \alpha(t) \sim Dirichlet(M(t)), \quad -2 \le t \le G_i$$

7.4.4 PCR+ or IgM+, no surveillance data. If the specified interval is defined by a PCR+ or IgM+ test at time  $t_2$  and the earliest possible date of infection was  $t_1$  (which might be marked by an IgM- result, or  $t_1 = t_2 - D$ ) then, if the cumulative persistence distribution (the probability that persistence is d or less weeks) is  $F(d,\theta)$  with parameter(s)  $\theta$ , then (dropping the  $\theta$ ):

Author: [name] (UNIVBRIS)

20

$$\pi_i(t) = \frac{F(t_2 - t)}{\sum_{t_1 \le u \le t_2} F(u - t)}, \text{ if } -2 \le t \le t_2, \text{ else } 0$$

7.4.5 PCR+ or IgM+ with surveillance data. Now we assume the same test results, but surveillance data is available as well:

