$$\pi_i(t) = \frac{\alpha(t)F(t_2 - t)}{\sum_{t_1 \le u \le t_2} \alpha(u)F(u - t)}, \text{ if } t_1 \le t \le t_2, \text{ else } 0$$

7.4.6 If the infant is congenitally infected, and we have PCR+ or IgM+ with surveillance data as above, we need only consider scenarios in which the maternal infection occurs during pregnancy. The summation in the denominator is therefore over:  $Max(t_1, -2) \le u \le Min(t_2, G_i)$ 

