#### A2.1 A single ZIKV IgM+ DENV IgM- test

To illustrate, we explore the implications of potentially false positive ZIKV IgM tests which cannot be attributed to DENV. To simplify we assume the DENV IgM is perfectly sensitive so that the -ve result rules out a DENV infection.

We assume a single ZIKV IgM+ DENV- test at week 20, and ask: what is the probability there has been a true maternal infection between weeks -2 and week 20, given a Z+D- IgM result at week 20? This quantity can be written as  $p(I_{Z,-2:20} \mid Z+D-_{20})$ . Let  $p(\overline{I}_{Z,-2:20})$  be the probability of no ZIKV infection between weeks -2 and 20. Using Bayes Rule, we expand the formula in section 7.4.5 to allow for imperfect test accuracy:

44

Author: [name] (UNIVBRIS)

$$\begin{split} p\Big(I_{Z,-2:20} \mid Z + D -_{20}\Big) &= \frac{p\Big(Z + D -_{20} \mid I_{Z,-2:20}\Big).p\Big(I_{Z,-2:20}\Big)}{p\Big(Z + D -_{20} \mid I_{Z,-2:20}\Big).p\Big(I_{Z,-2:20}\Big) + p\Big(Z + D -_{20} \mid \overline{I}_{Z,-2:20}\Big).p\Big(\overline{I}_{Z,-2:20}\Big)} \\ &= \frac{\displaystyle\sum_{-2 \leq u \leq 20} F(22 - u).Se\bigg(1 - e^{-\sum_{-2 \leq u \leq 20} \lambda(u)}\bigg)}{\displaystyle\sum_{-2 \leq u \leq 20} F(22 - u).Se\bigg(1 - e^{-\sum_{-2 \leq u \leq 20} \lambda(u)}\bigg) + (1 - Sp).e^{-\sum_{-2 \leq u \leq 20} \lambda(u)}} \end{split}$$

To calculate  $\pi_i(t)$  in this case, we have two components: one for the period up to the IgM+ result, the other after it:

$$\pi_{i}(t) = \begin{cases} \frac{\sum_{-2 \le u \le 20} F(22 - u).Se\left(1 - e^{-\sum_{-2 \le u \le 20} \lambda(u)}\right)}{\sum_{-2 \le u \le 20} F(22 - u).Se\left(1 - e^{-\sum_{-2 \le u \le 20} \lambda(u)}\right) + (1 - Sp).e^{-\sum_{-2 \le u \le 20} \lambda(u)}} & -2 \le t \le 20 \\ 1 - e^{-\lambda t} & 21 \le t \le G_{i} \end{cases}$$

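### The persistence distribution F is evaluated at three different elapsed times in SAP 7.4, 7.5 and A2.1, and the duration d is never defined well enough to say which is right

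*SAP*

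**What the plan says.** F is the cumulative distribution of persistence: 7.4.4 calls it "the probability that persistence is d or less weeks", 7.5.2 gives the same meaning, and 7.5 says it "is defined for d=1,2...D where D is the maximum possible duration of that marker". It is then used in three places.

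- **7.4.4 and 7.4.5** (dating an infection from a positive test at t2): the numerators of "\pi_i(t) = \frac{F(t_2 - t)}{\sum_{t_1 \le u \le t_2} F(u - t" and "\alpha(t)F(t_2 - t)}{\sum_{t_1 \le u \le t_2} \alpha(u)F(u - t" take F at t2−t.
- **7.5.1 and 7.5.3** (estimating F): the single-test likelihood is "F(W_{R_i} - T - 1, \theta) - F(W_{L_i} - T - 1, \theta", and the multiple-test version repeats the offset, "F_{k}(W_{Ri_{k}} - t - 1, \theta_{k}) - F_{k}(W_{Li_{k}} - t - 1, \theta_{k".
- **A2.1** (correcting for test accuracy): "We assume a single ZIKV IgM+ DENV- test at week 20". The text states that "we expand the formula in section 7.4.5 to allow for imperfect test accuracy", and then evaluates F at 22−u with u summed from −2 to 20.

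Four further rules bear on what d means. Section 7.5 takes tests as positive from the onset date. Section 7.4.4 allows an earliest onset of t1 = t2−D. Section 7.5.1 sets U_L = U_R−D when there is no initial negative, and W_R = W_L+D when there is no final negative.

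**The concern.** Section 3.2 says persistence, gestational age at infection and vertical transmission must be analysed together so that they are technically consistent, and 7.7 assembles them into one model. That fails if the component that estimates F and the components that apply it measure elapsed time differently. Such an offset is systematic and does not shrink with more women.

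It matters most for markers that last only a few weeks. Section 7.5.3 relies on those markers, since it treats short-persistence tests as highly informative about the longer ones. The definition of d also decides how a published persistence distribution is entered as a prior under 7.5.1.

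**Working it through.** **1. The three arguments side by side.** Let a = test week minus onset week.

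| Section | Printed argument | In terms of a |
|---|---|---|
| 7.4.4, 7.4.5 (numerator) | t2−t | a |
| 7.5.1, 7.5.3 | W−T−1, W−t−1 | a−1 |
| A2.1 (test at week 20) | 22−u = (20−u)+2 | a+2 |

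The gaps are 1 week (7.5 to 7.4), 2 weeks (7.4 to A2.1) and 3 weeks (7.5 to A2.1).

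**2. A2.1.** Putting t2 = 20 into 7.4.5 gives 20−u. The figure 22 would be right if u were re-indexed to run from 0 to 22, but the printed sum runs from −2 to 20. As printed, onset in week 20 (elapsed 0) is scored at F(2), and onset in week −2 (elapsed 22) at F(24).

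**3. What the −1 implies.** Two definitions of d are possible.

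- **(a) Positive in weeks T to T+d−1.** Positive at W_L means d > W_L−T; negative at W_R means d ≤ W_R−T. The likelihood is F(W_R−T) − F(W_L−T), with no −1.
- **(b) Positive in weeks T to T+d.** Positive at W_L means d ≥ W_L−T; negative at W_R means d ≤ W_R−T−1. The likelihood is F(W_R−T−1) − F(W_L−T−1), exactly as printed.

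**4. Which definition do the SAP's other rules follow?**

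- t1 = t2−D and U_L = U_R−D need a marker that can still be positive D weeks after onset. That is possible under (b), whose last positive week is T+D, but not under (a), whose last is T+D−1.
- d starting at 1 fits (a). Under (b), a woman positive in week T and negative in T+1 has d = 0 and gets F(0) − F(−1) = 0, although such a record can occur.
- W_R = W_L+D fits (a). With W_L = T, (a) gives F(D) − F(0) = 1, as it should when no final negative is seen; under (b) the printed form gives F(D−1), which is not 1.
- Positivity from the onset date fits both.

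The rules therefore point both ways.

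**5. Effect on estimated persistence.** 40,000 durations were simulated: Weibull, shape 2, rounded up to whole weeks, onset known, tests at onset and then every 1, 2 or 4 weeks. The 12-week mean is the SAP's IgM figure (8.2.3); the 3-week PCR mean, the shape and the spacing are assumptions. Fitted means, in weeks:

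| True mean | Definition generating the data | Printed likelihood (−1) | Without −1 |
|---|---|---|---|
| 3 | (a) | 2.1–2.2 | 3.0 |
| 3 | (b) | 3.0 | 3.9–4.0 |
| 12 | (a) | 11.0 | 12.0 |
| 12 | (b) | 12.0 | 13.0 |

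Under (a) with weekly tests and a mean of 3, the Weibull scale is 3/Γ(1.5) = 3.385, so 1 − exp(−(1/3.385)²) = 8.4% of women have zero likelihood under the printed form and were dropped from that fit. Under (b) with d ≥ 1 there are none.

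**6. Effect on dating.** IgM+ at week 20, flat incidence over weeks −2 to 20, Weibull mean 12 and shape 1.5, with 1−F as the probability of still being positive.

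| Case | Mean GA at infection | P(onset ≤ week 13) |
|---|---|---|
| (a), consistent throughout | 12.72 | 0.476 |
| (a), F one week short, applied at a | 12.91 | 0.462 |
| (a), F one week short, applied at a+2 | 13.23 | 0.437 |
| (b), consistent throughout | 12.51 | 0.491 |
| (b), applied at a | 12.72 | 0.476 |
| (b), applied at a+2 | 13.07 | 0.449 |

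Under either definition the 7.4 mismatch costs about 1.5 points (0.476−0.462 = 0.014; 0.491−0.476 = 0.015), and the A2.1 mismatch about 4 points (0.476−0.437 = 0.039; 0.491−0.449 = 0.042).

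**The case against.** The strongest reply is that the −1 is no error. Under (b) the printed likelihood is exact, it recovers the true mean, and deleting the −1 would lengthen persistence by about a week. Two of the SAP's limits on D support (b). If 7.4 were also rewritten as the probability that persistence is at least t2−t, it would agree with 7.5.1, leaving only A2.1 out of line. The timeline that introduces U_L, U_R, W_L and W_R is not shown in the text at hand and may settle the week convention. A2.1 is an illustration, and A2.3 leaves the method for sequences of tests open.

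Much of this stands. A reader might infer that 7.5.1 underestimates persistence by a week. The documents do not support that as a general statement, because it holds only if (a) is intended. A reader might also take the offsets in 7.5 and A2.1 as partly cancelling; step 6 shows that they compound.

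What does not stand is that nothing needs correcting. Definition (b) conflicts with d starting at 1 and with W_R = W_L+D. Section 7.4 as printed does not use the (b) form. The adjustments promised in 7.5 concern the onset date and immediate positivity, not the index. A2.1 fits neither definition.

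**Conclusion.** The inconsistency is real: one F, three elapsed-time scales. The 22−u in A2.1 is wrong under both definitions, by two weeks under (a) and three under (b). Whether 7.5.1 and 7.5.3 or 7.4 must change cannot be decided from the SAP, because its rules on D, W_R and the range of d contradict each other.

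The size depends on the marker. For an assumed 3-week PCR mean, choosing the wrong definition changes the estimate by about 0.8 to 1 week, roughly a third. For a 12-week IgM mean it is about 1 week, and the probability of onset by week 13 moves by only 1 to 4 points. These figures rest on the assumed Weibull shapes, test spacing, flat incidence and PCR mean.

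They also assume that 1−F replaces F in 7.4 and A2.1. Printing F where the probability of still being positive is needed is a separate and larger error (mean GA of about 5 weeks instead of 12.7 in the same example). Correcting it does not remove the offsets.

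**What to change.** Define d in one sentence in 7.4 or 7.5, and make every formula and limit follow it.

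- **If (a), positive in weeks T to T+d−1:** use F(W_R−T) − F(W_L−T) in 7.5.1 and the same form in 7.5.3; use 1−F(t2−t) in 7.4 and 1−F(20−u) in A2.1; limit t1 and U_L to D−1 weeks back.
- **If (b), positive in weeks T to T+d:** keep the −1 in 7.5.1 and 7.5.3; use 1−F(t2−t−1) in 7.4 and 1−F(20−u−1) in A2.1; allow d = 0; set W_R = W_L+D+1.

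State as well that published persistence distributions will be converted to the chosen scale before they are used as priors. The cost is one definition and the correction of a few formulas before coding. Data collection is not affected.
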